## 4 Study Design

### Overview of study approach

This is a multi-site national study (8 U.S. cities), where up to 1000 HCV-infected PWIDs (injecting illicit substances within 3 months of screening) will be randomized to either PN plus weekly or biweekly blister pack dispensation versus mDOT. Among patients who go on to initiate HCV treatment (n=600 targeted) with a once-daily combination regimen of fixed-dose sofosbuvir/velpatasvir, a comparison will be conducted of the proportion of patients in each arm who: (a) optimally adhere ( $\geq 80\%$ ), (b) complete treatment, (c) achieve SVR, and (d) develop resistance. The primary outcome will be SVR. The 8 sites offer geographic and policy diversity: New York City, Baltimore, Providence, Boston, Morgantown, Seattle, San Francisco, and Albuquerque.

Participants will be recruited from diverse venues: OTPs, community health centers, syringe exchange programs, community-based organizations, homeless programs, and cohorts established by research studies. The clinical sites will determine eligibility based on clinical records, or on-site testing including HCV tests (anti-HCV and HCV viremia). Study participants will be screened, consented and enrolled on-site at OTP and non-OTP settings. There will be differences in linkage, engagement and outreach at each site. These procedures will be documented in site specific operating manuals.

Patients will be randomized to one of two models of care: patient navigation (PN) vs. modified directly observed treatment (mDOT). Patients enrolled from OTPs who are receiving methadone and randomized to mDOT will receive doses of once daily medication at the same time as they receive methadone. Patients enrolled from community health settings and randomized to mDOT may receive observed doses through use of miDOT (emocha Mobile Health, Inc.), a mobile health app on a smartphone, or at the CHC. Subjects randomized to PN will receive a standardized PN intervention. Sites also have the option to offer all subjects optional additional support through a peer-led support group.

Participants will be followed for up to 180 weeks: 12 weeks of pre-treatment evaluation, 12 weeks of treatment, 12 weeks of follow-up to determine SVR12, and 144 weeks of follow-up to determine long-term SVR and reinfection. Data sources will include clinical lab and imaging results from medical records, blood tests (HCV viral load during long-term follow-up and resistance assays), urine toxicology, questionnaires, electronic monitors for assessing adherence, and interviews.

## 5 Study Population

Participants will be recruited from a diverse national patient population from at least 16 health centers in 8 states- all with on-site HCV care (8 OTPs and 8 community health centers – **Table 1**). Target enrollment is up to 1000 PWID (to target 600 PWID initiating treatment) with the following characteristics (**Table 2**): Caucasian (55%), Latino (21%), and African American (20%), male (61%), and mean age of 44 years; 28% will be HIV/HCV co-infected. Within the 8 OTPs, there is a potential pool of 4790 mono-infected and 510 co-infected patients. Within the 8 community health centers, there is a potential participant pool of 2809 mono-infected and 1433 co-infected patients.

Community enrollment has a pool of >4000 HCV-infected clients in the community. With over 13,000 HCV-infected patients, target enrollment is 1000 PWID. Eligibility for HCV treatment will be determined by subjects' on-site medical care providers, as part of routine clinical care.

**Table 1: HCV-infected Patients at OTPs and Community Health Centers**

City, State	OTP	#HCV	#HIV/HCV	Community Health Center	#HCV	#HIV/HCV
Bronx, NY	Melrose Wellness Center	1500	250	Comprehensive Health Care Center	400	60
Providence, RI	CODAC Behavioral Health Services	750	25	Miriam Hospital Brown Infectious Diseases Center	50	400
Albuquerque, NM	UNM ASAP	720	25	Truman Health Services	20	200
San Francisco, CA	Ward 93 Opiate Treatment Outpatient Program	325	70	PHP Ward 86 and Tom Waddell Urban Health Clinic	100	213
Boston, MA	Bay Cove Human Services	150	10	MGH and CCHI	300	100
Baltimore, MD	Reach Health Services	300	60	Comprehensive Care Practice	1000	100
Seattle, WA	Evergreen Treatment Services	700	50	Harborview Adult Medicine	884	250
Morgantown, WV	Valley Alliance Treatment Services	345	20	Milan Puskar Health Right	110	20
Total		4790	510		2809	1433

**Table 2: Demographic, Clinical, and Psychosocial Characteristics of HCV-infected Patients**

State	NY	MA	RI	WV	WA	NM	CA	MD	Total
Age (mean)	49.0	40.5	55.0	30.0	40.0	41.5	48.0	46.5	43.9
Gender									
Male	62% (78)	68% (85)	41% (51)	55% (69)	63% (78)	70% (88)	82% (102)	50% (63)	61% (614)
Ethnicity									
Latino	65% (81)	13% (16)	15% (19)	0% (0)	5% (6)	52% (65)	17% (21)	1% (1)	21% (213)
Race/ethnicity									
Caucasian	20% (25)	73% (91)	37% (46)	98% (118)	62% (78)	76% (95)	50% (63)	25% (31)	55% (546)
African-Am	25% (31)	20% (25)	31% (39)	2% (1)	24% (30)	3% (4)	25% (31)	75% (65)	20% (196)
Native-Am	0% (0)	1% (1)	11% (14)	0% (0)	2% (3)	9% (11)	1% (3)	0% (0)	3% (32)
Asian	0% (0)	1% (1)	0% (0)	0% (0)	2% (3)	1% (1)	4% (5)	0% (0)	1% (13)
Other	55% (69)	5% (6)	21% (26)	2% (3)	10% (13)	11% (14)	20% (25)	0% (0)	21% (211)
Cirrhosis	34% (43)	15% (19)	45% (56)	7.5% (9)	15% (19)	33% (41)	14% (18)	5% (6)	21% (211)
HIV-infected	20% (25)	13% (16)	50% (62)	2.0% (3)	5% (6)	47% (59)	70% (88)	13% (16)	28% (336)
Unstably housed	20% (25)	35% (44)	11% (14)	13% (16)	28% (35)	25% (31)	60% (75)	15% (19)	26% (261)
Psych	75% (94)	67% (84)	63% (78)	45% (54)	60% (75)	35% (44)	71% (89)	25% (31)	55% (549)

The participants in the proposed trial will be 1000 patients recruited from 8 cities: Bronx (Montefiore Medical Center), Baltimore (John Hopkins University), Providence (The University of Rhode Island), Boston (Harvard School of Medicine), Morgantown (West Virginia University), San Francisco (UCSF), Albuquerque (University of New Mexico), and Seattle (University of Washington).

## 5.1 Inclusion Criteria

Inclusion criteria that must be met before enrollment:

- Current HCV infection (HCV viremic)
- HCV Viral load test from any time
- Must have had the following tests performed in the past 12 months: AST, ALT, platelets
- Actively injecting drugs (any substance within 3 months of screening)
- Not previously treated with HCV direct-acting antiviral medications
- Age 18 – 70
- Willing to receive HCV treatment with sofosbuvir/velpatasvir
- Willing to be randomized to either PN vs mDOT
- If receiving methadone, be attending or be willing to attend OTP a minimum of 5 times per week

- Able to provide informed consent
- English or Spanish fluency

## 5.2 Exclusion Criteria

Exclusion criteria will include:

- Pregnant or breast feeding
- Hepatocellular carcinoma

## 5.3 Re-Screening

Subjects can be rescreened if they fail screening. Participants can be rescreened only one time following first screen failure.

## 5.4 Randomization

Up to 1000 patients will be recruited, with patients randomized to PN or mDOT in a 1:1 ratio (500 subjects in each group) in variable block sizes of 2-6 via central, computer-generated randomization provided by the UNM Statistical and Data Coordinating Center (SDCC). Randomization will occur in blocks to ensure comparison groups of approximately equal size. Given that the intervention will not be blinded, block size will vary to prevent anticipation of treatment arm assignment.

Two special randomization strategies (stratification and blocking) will be used to avert imbalances in prognostic factors or treatment settings, and to ensure comparison groups of approximately equal size. Participants will be stratified by 3 factors: city, OTP vs. community health center and stage of liver disease (cirrhosis v. no cirrhosis).

In addition, adaptive re-weighting of random allocation in a pseudo urn randomization fashion will be made when N~300 has been enrolled to balance the sample size between mDOT and PN arms. Specifically, as we hypothesize that number of randomized subjects who will initiate treatment will be larger in the PN arm, unbalancing between arms is likely to occur during the course of the study. Of note, therefore, a randomized subject will not necessarily be a clinical treatment subject but will be included in the comparison of treatment initiation.

To adjust for this potential unbalance, we will adjust randomization based on observed allocation ratio at the middle of trial if the overall allocation difference is greater than 5% (i.e., <47.5% vs. 52.5%).

Storage and dispensing of random allocation codes will be made in a centralized fashion. The UNM SDCC will generate and store the codes for all sites and types of clinics, and will be embedded into the Research and Electronic Data Capture (REDCap) data management system in the backend so that the identification of a treatment assignment will be ready and immediate without contacting the coordinating center when requested through the REDCap electronic request form by a responsible research staff at the sites whenever a new eligible participant is enrolled. The UNM SDCC will also be responsible for conducting re-weighted randomization, if necessary, at the middle of the trial.

Randomization will occur at enrollment, however research staff will wait until after the baseline assessments have been conducted to reveal the randomization to the participant, to avoid bias during baseline data collection.

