### 8.1.2 Visit 0: Eligibility confirmation, Consent and Enrollment Visit

A research assistant will meet with the potential participant in a private room in OTP, community health center, or other research location to confirm eligibility and obtain consent. Depending upon the time the participant has available and their state, this visit may be combined with Baseline Visit.

- Discuss study procedures, risks and benefits of study participation
- Obtain written signed consent for:
  - 1) Clinical trial participation;
  - 2) Study staff to use protected health information from clinic records;
  - 3) Study staff to disclose protected health information in event of clinical need
  - 4) staff to track any hospitalizations or emergency events

- Administer the sociodemographic instrument.
- Participant will be randomized to the DOT or PN arm (stratified, blocked) generated by DCC at UNM HSC. Wait until after baseline assessments have been completed before revealing randomization status to the participant.
- If the Baseline Visit is not taking place at this time, schedule the Baseline Visit within two weeks of enrollment.
- Treatment initiation should begin within twelve weeks of enrollment

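### The protocol withholds the arm only from the participant, so it does not ensure that the research assistants who run the baseline interviews are unaware of it

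*Protocol*

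**What the plan says.** Protocol 5.4 fixes the timing: "Randomization will occur at enrollment". Under the same section "the identification of a treatment assignment will be ready and immediate without contacting the coordinating center when requested through the REDCap electronic request form", and the person who makes that request is a member of the site's research staff. Section 8.1.2 lists randomization as a Visit 0 step, after the sociodemographic survey.

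The baseline interview may take place on the same day. Otherwise, "If the Baseline Visit is not taking place at this time, schedule the Baseline Visit within two weeks of enrollment". Section 8.2 has research assistants administer the Visit 1 instruments. Research staff then tell the participant the arm at that visit.

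Concealment is described in one direction only. Section 5.4 provides that "research staff will wait until after the baseline assessments have been conducted to reveal the randomization to the participant"; the reason given is bias in the baseline data. Sections 8.1.2 and 8.2 repeat the restriction for the participant. The trial is open label. Its other allocation safeguard is the varying block size: "Given that the intervention will not be blinded, block size will vary to prevent anticipation of treatment arm assignment".

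**The concern.** Withholding the arm from the respondent deals with one source of bias in an interview. The interviewer is another, because an interviewer who knows the arm may probe, prompt or code differently. The varying block size does not help here. It makes the next assignment harder to predict, but it does not hide one already issued.

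What is at stake is the covariate part of the primary model. SAP 5.4 compares baseline characteristics between arms among initiators and adds any with p<0.01 to the mITT model. The purpose is to catch imbalance that arises because the two models of care may trigger initiation in different kinds of people. A difference produced by arm-aware interviewing would look the same to that screen. Several of the same items also define subgroups in SAP 6.1, and some Visit 1 scales supply the starting value for change-based mediators (Protocol 11.12.3, SAP 7).

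**Working it through.** There is no plan figure to reproduce. The check is on order, access and use.

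**Order and access**

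1. The arm exists from Visit 0 (Protocol 5.4 and 8.1.2).
2. It is available to site staff from then. It is "requested through the REDCap electronic request form by a responsible research staff at the sites whenever a new eligible participant is enrolled", and the system returns it at once.
3. The interview follows 0 days later (combined visit) to 14 days later (8.1.2, 8.2). Two weeks is a maximum.
4. A research assistant conducts Visit 0, and research assistants administer the Visit 1 instruments. The same role is named twice, and no separation of persons is required.
5. Every concealment instruction (5.4, 8.1.2, 8.2) concerns the participant. None masks the interviewer, names a different requester, or has REDCap hold the result until the baseline forms are finished.

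**Which items are exposed, and where they are used**

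| Item | Collected | Use in the SAP | Open to interviewer influence |
|---|---|---|---|
| PHQ-9, GAD-7, hazardous alcohol use, recent medication for opioid use disorder, times injecting per day | Visit 1 interview | Table 1 (baseline visit the only source) and subgroups in 6.1 | Yes |
| Days injected, substances injected | Visit 1 interview | Table 1; not in the 6.1 list | Yes |
| Shame, social support, self-efficacy | Visit 1 interview | Candidate mediators in section 7; not in Table 1 or 6.1 | Yes, exploratory use only |
| Urine toxicology | Visit 1 test | Table 1 and 6.1 | Little |
| Sociodemographic survey | Visit 0, listed before randomization | Table 1 and 6.1 | No |
| Last injection | Screening | Table 1 and 6.1 | No |
| Cirrhosis, viral load, genotype, HIV | Chart review | Table 1; most also in 6.1 | Little or none |
| SVR | Laboratory viremia (SAP 5.2) | Primary outcome | No |

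Two qualifications apply to the third row. Protocol 11.6 names social support among the variables to compare between arms, and SAP 4.1 marks its list as still to be settled. Protocol 3.3 also plans to relate shame, stigma and social support to outcomes. As the SAP stands, however, none of these scales enters the p<0.01 screen.

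**Loss between Visit 0 and Visit 1**

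- Treatment starts after the baseline visit (Protocol 8.3). A randomized person who never attends Visit 1 therefore cannot, under the protocol, enter the mITT or per-protocol sample.
- That person stays in the ITT sample (SAP 3.2), where an undetermined SVR counts as failure, and is a non-initiator in the treatment-initiation comparison (SAP 8.1).
- Only the Visit 1 data are missing. Screening data, Chart Review Part 1 and the sociodemographic survey already exist, and Chart Review Part 2 is done at 12 weeks whether or not treatment starts (Protocol 8.4).
- The ITT model adjusts for site, clinic type and cirrhosis (SAP 5.4). None of these comes from the Visit 1 interview.

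The documents do not give the number lost. As an illustration only, assume a loss of 3% to 5%, equal in both arms, and take the SAP Table 1 column totals as the randomized sample: 375 + 379 = 754.

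- Number lost: 0.03 × 754 ≈ 23 to 0.05 × 754 ≈ 38.
- An ITT risk difference is multiplied by 1 − f, where f is the fraction lost. A 9-point difference would shrink by 9 × 0.03 = 0.27 to 9 × 0.05 = 0.45 points.

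This applies to the secondary ITT analysis only.

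**The case against.** The strongest reply is that the documents never say the person who requests the assignment also conducts the interview. REDCap access rules could sit in the Data Management Plan, the Manual of Procedures or the site operating manuals, none of which is available here. That stands. A reader might infer that baseline data were in fact collected by unblinded assessors, but the documents show only that masking is not required or described.

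Second, the scales are largely self-report, so keeping the respondent unaware removes a real source of bias. That stands as well. The aim is partly met.

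Third, the trial is open label by design and SVR is a laboratory result. This limits the consequence to covariates, subgroups and mediators. It does not answer the point for those.

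Fourth, keeping early losses in the denominator is deliberate. Protocol 5.4 includes non-initiators in the initiation comparison, and SAP 3.3 uses the ITT sample for cascade milestones. This is a fair cost to set against moving randomization. The cost to the arm comparison is small, because participants do not learn their arm before the baseline interview ends. The cost to the description of the cascade is real and calls for separate reporting.

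Fifth, the SAP expected main outcome collection to finish by April 2020 and already shows arm totals. For participants already randomized, only reporting can help.

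**Conclusion.** The point holds as a gap in the safeguard: the protocol does not ensure that baseline interviewers are unaware of the arm, for a period of 0 to 14 days before the interview. The conclusion rests on the text of Protocol 5.4, 8.1.2 and 8.2. It assumes that no document outside these two closes the gap.

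Neither the direction nor the size of any interviewer effect can be derived from the documents. The route to the primary analysis is indirect. An exposed Visit 1 item would have to differ between arms at p<0.01 among initiators, and so enter the mITT model.

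Three stronger readings are not supported:

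- **All baseline data are compromised.** Survey, screening, chart and urine data are little affected or unaffected.
- **Stigma, shame, efficacy and social support drive covariate selection.** They are not in SAP Table 1 or the SAP 6.1 list.
- **Loss before Visit 1 dilutes the primary SVR contrast.** Those participants cannot be in the mITT sample, and the illustrative 3% to 5% is an assumption.

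This is an inexpensive improvement to the design and does not threaten the primary result.

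**What to change.** Choose one of two changes to Protocol 5.4 and 8.1.2:

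- **Move randomization** to after the Visit 1 instruments are complete.
- **Keep randomization at enrolment** but have REDCap withhold the assignment from site staff until the baseline forms are complete.

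Either works on the same day when Visits 0 and 1 are combined. The cost is a wording change and a form-completion rule in REDCap, with no added visits. If randomization itself moves, enrolled participants lost before Visit 1 leave the randomized denominator and should be reported as a separate step in the care cascade. Withholding the result in REDCap leaves the denominator unchanged.

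For participants already randomized, report whether baseline interviewers had access to the assignment, and Visit 1 non-attendance by arm. If an exposed Visit 1 item passes the p<0.01 screen, it would also help to show the mITT odds ratio with and without it. This uses data already held.

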## 5.5 Withdrawal

### Reasons for Withdrawal

Subjects may withdraw or be withdrawn for any of the reasons given below. The reason for withdrawal will be recorded on a CRF.

In accordance with the current revision of the Declaration of Helsinki (amended October 2000, with additional footnotes added 2002 and 2004) and any other applicable regulations, a subject has the right to withdraw from the study at any time and for any reason and is not obliged to give his or her reasons for doing so. The Investigator may withdraw the subject at any time in the best interests of the subject's health and well-being. In addition, the subject may withdraw/be withdrawn for any of the following reasons:

- Administrative decision by the Investigator.
- Ineligibility (either arising during the study or retrospective, having been overlooked at screening).
- Significant protocol deviation.
- Subject non-compliance with study requirements.

## 6 Investigational Interventions

This is multi-site national study (8 U.S. cities), where up to 1000 HCV-infected PWIDs (injecting illicit substances within the last 3 months) will be randomized to either PN plus blister pack dispensation (weekly or every other week) versus mDOT.

### 6.1 modified Directly Observed Treatment

#### 6.1.1 OTP Setting

Observation of HCV medication administration will be linked to methadone visits among patients receiving methadone. The schedule of five days per week will be considered modified DOT (mDOT). Participants enrolled in the mDOT arm through the OTP who are not taking methadone, but another version of opioid agonist treatment (OAT), such as buprenorphine, will follow the mDOT protocol for community health center participants.

*Method of observation:* Subjects in the mDOT arm will receive: 1) 5 directly observed doses per week (from a blister pack) at the same time as they receive methadone, and 2) take-home doses packaged in blister packs for self-administration on other days. In addition, the observing staff will: (i) notify clinicians when doses are declined or missed and (ii) refer subjects to clinicians as necessary.

*Administration of Medication:* Medications will be packed in labeled blister packs. For participants who are receiving methadone and attending clinic 5 days/week, medication will be kept at the clinic where research/clinical staff will observe them taking the medications. Participants will also receive take-home doses packaged in blister packs for the days that they are not observed at the methadone clinic. Blister packs will be returned to research staff at the next research visit.

Each time a subject misses an observed dose, there should be an assessment by the observer: the observer will ask whether the patient missed that day's dose, took a rescue dose, or took medication from another source.

*Rescue Doses:* Each participant will receive a container labeled with the contents, containing up to two doses of HCV treatment medication. In the event the participant misses the opportunity to take an observed dose at the OTP, they can take one of the rescue doses instead. This container will be either a pill case or a container specified by the local site. When the participant presents to the program for the next observed dose, the prior missed dose will be given to the participant to replace the rescue dose that was taken for any future events.

*Record keeping:* Each time a subject misses an observed dose, there should be an assessment by the observer: the observer will ask whether the patient missed that day's dose, took a rescue dose, or took medication from another source.

Staff that observe the participant taking their medication will log the information on a standardized log. Adherence will be measured with standardized forms each week by Study Coordinators and will include pill counts of blister packs.

Participants that choose to leave the OTP during treatment will have the potential to remain in the study by being transferred to the Community Health Center.

